4.5 Early Withdrawal of Subjects

4.5.1 When and How to Withdraw Subjects

A subject may withdraw from the study at any time and for any reason. Discontinuation of therapy will not affect the subject's relationship with the treating physician. It is intended that subjects will be treated until investigator-determined progressive disease (radiologic or clinical deterioration) or unacceptable toxicity. Reasons for withdrawal from treatment include, but are not limited to: progressive disease as determined by RECIST v1.1, clinical deterioration, adverse events, protocol violation, non-compliance, withdrawal of consent, investigator or sponsor decision, or if the subject is lost to follow-up. Withdrawal from the study can be made in writing to the Principal Investigator, [name]. Any samples/specimens remaining after formal withdrawal, will be destroyed/discarded per Institutional guidelines.

4.5.2 Data Collection and Follow-up for Withdrawn Subjects

When a subject is discontinued from treatment for any reason, they are to undergo the assessments in the end of treatment visit within 4 weeks of the last dose. All subjects who discontinue treatment as a result of an adverse event must be followed until resolution or stabilization of the adverse event. If a subject withdraws from study treatment, attempts should be made to contact the subject to determine the reason(s) for discontinuation. The subject will continue to be followed for survival information every 3 months after completion of the End of Treatment visit. All subjects, including subjects who discontinue treatment for other reasons than progressive disease per RECIST 1.1, should undergo a scan to assess disease status prior to termination from the study.

If a subject does not return to the clinic for the end of treatment visit or is not reached for overall survival follow-up, at least 3 documented attempts, including one via certified mail, should be made to contact the subject. If the subject does not respond to these requests, the date of death should be captured from public records.

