3.2 Primary Study Endpoints

For Phase Ib, the primary endpoint is identification of toxicities, tolerability and definition of a recommended phase II dose (RP2D) of Q3WK infusions of CDX-3379 in combination with once daily oral administration of trametinib.

For Phase II, the primary endpoint is an estimation of the overall response rate and duration of response in patients treated with CDX-3379 in combination with trametinib in *NRAS* mutant and WT melanoma.

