3.3 Secondary Study Endpoints

For Phase 1b, the secondary endpoints are to assess clinical activity and steady-state pharmacokinetics of CDX-3379 and trametinib

For Phase II, the secondary endpoints are description of antitumor activity of the combination CDX-3379 and trametinib and include progression free survival (PFS) and overall survival (OS).

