6.6 Survival Follow-up

Survival data will be collected via telephone or clinic visits every 3 months (± 10 days) from the date of last treatment (date of last treatment is calculated from the last dose of trametinib) until death, loss to follow-up, withdrawal of consent, study termination by the Sponsor, or up to 5 years. In addition, any new anti-cancer therapies and procedures should be collected and documented. Should subjects refuse or drop out of survival follow-up, attempts should be made to obtain any death information via public records whenever possible.

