6.7 Schedule of Assessments Summary

Procedure	Screening	Cycle 1 ⁴			Cycle 2 ⁴			Additional cycle ⁴			Every 12 weeks or sooner, at the discretion of the physician	End of Treatment (EoT) ⁸	Survival Follow-up ¹²
		Wk 1	Wk 2	Wk 3	Wk 1	Wk 2	Wk 3	Wk 1	Wk 2	Wk 3			
Informed Consent	X												
Medical History	X												
Demographics	X												
Physical Exam	X	X	X		X	X		X				X	
Vital Signs	X	X			X			X				X	
ECOG PS	X	X			X			X				X	
CBC	X	X			X			X				X	
Serum Chemistry ¹³	X	X			X			X				X	
Tumor Biopsy	X												
	X												

CONFIDENTIAL

This material is the property of the NYU School of Medicine and Langone Medical Center. Do not disclose or use except as authorized in writing by the study sponsor

Baseline imaging within 4 weeks prior to enrollment (CT/PET-CT/MRI)													
Pregnancy Test (Urine)	X	X			X			X					
EKG	X	X ₁₁			X ₁₁			X ₁₁					
Archived tumor	X												
Fresh Core Biopsy	X ₂		X ₃	X ₃								X	
Pharmacokinetic blood samples		X ₁₀	X		X ₁₀	X		X				X	
Immunogenicity sample		X			X							X	
Concomitant meds	X	X	X		X			X				X	
CDX-3379 dosing ¹⁶		X			X			X					
Trametinib dosing		X	X	X	X	X	X	X	X	X			
AE assessment and reporting		X	X		X			X				X	
Disease evaluations ^{5,7}	X										X ₉	X ₁	
Overall Survival Reporting ⁶													X
Echocardiogram/MUGA ¹⁵	X										X		
Ophthalmologic Exam ¹⁴	X	X			X			X					

Footnotes:

- 1 = Unless performed in the prior 6 weeks as part of a previous visit
- 2= prior to first treatment with CDX-3379 and trametinib
- 3= performed between days 14-16
- 4= All procedures should occur ±2 calendar days from scheduled date of visit
- 5 = Disease evaluation per RECIST version 1.1.
- 6 = Should patients refuse or drop out of survival follow-up, attempts should be made to obtain any death information available via public records.
- 7 = Upon disease progression determination
- 8 = End of treatment visit should be completed within 4 weeks of the last dose of study drug
- 9 = end of treatment biopsy/disease progression. Should occur within 4 weeks of last treatment.
- 10 = PK blood samples are collected predose before CDX-3379, immediately following CDX-3379 infusion, and 1 hour post dose following trametinib
- 11= one reading prior to the start of CDX_3379 infusion
- 12= Survival data will be collected via telephone or clinic visits every 3 months (±10 days) from the date of last treatment until death, loss to follow-up, withdrawal of consent, or study termination by the Sponsor

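### After a stop without RECIST progression, the schedule collects no further progression data, in conflict with sections 6.4 and 7.2, so duration of response and PFS lose events

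*Combined protocol and SAP*

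**What the plan says.** Section 3.2 states that for phase II "the primary endpoint is an estimation of the overall response rate and duration of response". Section 3.3 makes PFS and OS secondary.

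Section 4.5.1 allows treatment to end without RECIST progression: "Reasons for withdrawal from treatment include, but are not limited to: progressive disease as determined by RECIST v1.1, clinical deterioration, adverse events", followed by non-compliance, withdrawal of consent and investigator or sponsor decision, among others.

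For patients who have stopped:

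- Section 6.5 asks for a disease evaluation at the End of Treatment visit, within 4 weeks of the last dose.
- Section 4.5.2 says all subjects, including those stopping for reasons other than RECIST progression, "should undergo a scan to assess disease status prior to termination from the study". On follow-up after treatment it says: "The subject will continue to be followed for survival information every 3 months after completion of the End of Treatment visit".
- Section 6.6 collects survival by telephone or clinic visit, and adds: "In addition, any new anti-cancer therapies and procedures should be collected and documented". It mentions neither imaging nor progression status.
- In the section 6.7 table, the survival follow-up column holds only overall survival reporting. Footnote 1, attached to the End of Treatment disease evaluation, reads: "Unless performed in the prior 6 weeks as part of a previous visit".

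Two other places point towards continued assessment. Section 6.4 sets disease evaluation at 12-week intervals counted from the first CDX-3379 dose and gives no end point. Section 7.2 says patients are followed to death for PFS and OS. Its only censoring rule is that patients still alive are censored at the time of evaluation. It gives no definition of duration of response and no rule for a stop without progression.

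**The concern.** Duration of response and PFS both need a progression date whether or not the patient is still on treatment. A site working from the visit schedule would stop recording disease status at End of Treatment, while a statistician working from section 7.2 would expect it to continue. If the schedule is what happens, a responder who stops for toxicity while still in response has no recorded end of response other than death, and a non-responder who stops has no later radiological progression date. Stops for intolerance need not be independent of prognosis, so the loss could also bias the estimates. Section 7.2 defers detailed methods to a statistical analysis plan to be completed before database lock. That plan can define censoring, but it cannot recover dates that nobody recorded.

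**Working it through.** The plan states no precision, event count or sample size for duration of response or PFS, so there is no figure to reproduce. The check is a reading of the sections, followed by an illustration of size.

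**1. Which sections collect progression after a stop?** Section 6.5 gives one evaluation. The section 4.5.2 scan is also a single one, most naturally the same one. Section 6.6 and the survival column of 6.7 give none. Section 6.4 and the 12-weekly column of 6.7 could be read as continuing, and section 7.2 implies that they do, but no post-treatment visit carries them out. The sections conflict, and the operational ones are those a site will follow.

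**2. The waiver.** Section 6.1 allows the baseline scan up to 4 weeks before enrollment and makes screening Visit 1. Footnote 1 does not require the earlier scan to be post-baseline. Example: baseline 1 week before enrollment and End of Treatment visit 4 weeks after it. The scan is 1 + 4 = 5 weeks old, inside the 6-week window, so the footnote would waive the evaluation that section 4.5.2 asks for in all subjects. A 12-week interval is 84 days, about 2.8 months. For a patient who stops before week 12, the End of Treatment evaluation may therefore be the only post-baseline one.

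**3. How often a responder would be affected.** Assume a share f stops without progression, independently and at the same rate in responders. The only related level in the documents is the 30% toxicity-discontinuation pause trigger in section 3.1. That is a safety threshold across groups, not a forecast. The chance that at least one of r responders is affected is 1 - (1 - f)^r.

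- r = 3 (smallest count passing stage 1 in section 7.2): 1 - 0.8^3 = 49% at f = 0.2; 1 - 0.7^3 = 66% at f = 0.3.
- r = 4 (what the section 3.1 wording would require): 59% and 76%.
- r = 10 (count required at 36 patients): 89% and 97%.

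**4. Possible bias in median PFS, if patients are censored at the stop.** Assume exponential times, with an on-treatment median of 2.8 months (the section 7.2 historical figure for *NRAS* mutant disease, borrowed here), so L = ln 2 / 2.8 = 0.2476 per month. The stop hazard giving share f is d = L f/(1 - f): 0.0619 at f = 0.2 and 0.1061 at f = 0.3. Let the off-drug hazard be kL. True PFS is

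S(t) = exp(-(L+d)t) + d [exp(-kLt) - exp(-(L+d)t)] / ((L+d) - kL).

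Check at f = 0.3, k = 2, t = 2.54: L + d = 0.3536 and kL = 0.4951. The exponentials are 0.4073 and 0.2843, and d/((L+d) - kL) = -0.75. So S = 0.4073 - 0.75 × (0.2843 - 0.4073) = 0.4995, and the true median is 2.54.

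- k = 1, any f: 2.80, no bias.
- f = 0.2, k = 1.5: 2.70.
- f = 0.3, k = 2: 2.54.
- f = 0.3, k = 3: 2.39.

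The Kaplan-Meier median censored at the stop is 2.8 throughout. The overstatement is 2.80 - 2.70 = 0.10 to 2.80 - 2.39 = 0.41 months, or 4% to 17%. With a 2.0-month median (wildtype), f = 0.3 and k = 2 give a true 1.81.

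**5. Scale.** With 19 exponential events, a rough 95% interval around 2.8 is 2.8 × exp(±1.96/√19), about 1.8 to 4.4 months. The modelled bias is small beside that.

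**The case against.** The strongest reply is that the plan never says assessment ends. Section 6.4 counts the 12-week interval from first dose, the 6.7 table gives disease evaluation its own column outside the treatment cycles, section 7.2 promises follow-up to death for PFS, and the section 4.5.2 scan is due only before leaving the study, which under section 6.6 could be up to 5 years later. This stands to the extent that the fault is a contradiction between sections, not a settled decision to stop imaging. It does not remove the problem, because no post-treatment visit schedules a scan or a progression field.

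Three stronger readings are tempting, and the documents do not support them.

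- A reader might infer that duration is censored at the stop as the plan is written. No text says so. Censoring at the stop, counting the stop as the end of response, and running on to death act in different directions, so no direction of bias is shown for duration of response.
- A reader might infer that a patient stopped for clinical deterioration soon after a scan is never imaged. Section 4.5.2 asks for a scan in all subjects. Section 4.5.1 also says "subjects will be treated until investigator-determined progressive disease (radiologic or clinical deterioration) or unacceptable toxicity", so such a patient may already count as progressed. That section lists clinical deterioration separately from RECIST progression as well, so its status for the endpoint needs stating.
- A reader might take the 30% trigger as an expected stop rate, or the modelled bias as a finding. Neither the stop rates nor the off-drug hazards come from the documents.

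It is also fair that no formal decision rests on this. The decision rule counts responses, duration of response is for estimation, and the Study Summary treats the comparison with historical PFS as exploratory. Deaths are still captured, and a censored responder still contributes observed time.

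**Conclusion.** The concern holds in a limited form and should be fixed. The operational sections provide at most one more disease evaluation after a stop without RECIST progression, and they conflict with sections 6.4 and 7.2. If the schedule is followed, duration of response and PFS lose progression events. Whether they are also biased depends on the off-drug hazard and on a censoring rule that is not written. Under the assumed 20-30% stopping and 1.5- to 3-fold hazard, with censoring at the stop, median PFS is overstated by 0.10 to 0.41 months; with an unchanged hazard there is only lost information. The response-count rule is largely unaffected. The reading of the sections is firm; the size is illustrative only.

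**What to change.** - Reconcile sections 4.5.2, 6.4, 6.6, 6.7 and 7.2 so that, after a stop without RECIST progression, disease status continues to be collected on the 12-week schedule from routine-care imaging, until RECIST progression, new anti-cancer therapy, death or withdrawal of consent.
- Add progression status, date and method to the existing 3-monthly contact.
- Limit the footnote 1 waiver to post-baseline scans, so that it agrees with section 4.5.2.
- In section 7.2, define duration of response, and state how it and PFS are censored for these patients, including how clinical deterioration, new therapy and a later death count.

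The cost is amendment wording, a short addition to one form and a little more data abstraction. Routine-care scans may fall at irregular times, so some progression dates will be less exact than on-study ones. Mandating extra study scans would be an added patient procedure and is not needed for this repair.

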4.5.3 Premature Termination or Suspension of Study

This study may be temporarily suspended or prematurely terminated if there is sufficient reasonable cause. Written notification, documenting the reason for study suspension or termination, will be provided by the suspending or terminating party to the investigator, funding agency, the IND sponsor and regulatory authorities. If the study is prematurely terminated or suspended, the PI will promptly inform the IRB and will provide the reason(s) for the termination or suspension.

Circumstances that may warrant termination or suspension include, but are not limited to:

- Determination of unexpected, significant, or unacceptable risk to participants
- Demonstration of efficacy that would warrant stopping
- Insufficient compliance to protocol requirements
- Data that are not sufficiently complete and/or evaluable
- Determination of futility

Study may resume once concerns about safety, protocol compliance, data quality are addressed and satisfy the sponsor, IRB and/or FDA.

CONFIDENTIAL

5 Study Drug

5.1 Description

5.1.1 CDX-3379 -Description, Packaging, and Labeling

Detailed technical information regarding CDX-3379 is provided in the Investigator's Brochure.

CDX-3379 is a human IgG1 λ mAb that specifically binds ErbB3 at a unique epitope and locks ErbB3 in an auto-inhibited configuration making the ErbB3 incapable of binding ligand or dimerizing with known tumor growth drivers such as HER2 and possibly EGFR.

CDX-3379, manufactured by MedImmune for Celldex, is supplied as a clear to opalescent, colorless to brown-yellow liquid, free from or practically free from visible particulates. CDX-3379 will be provided at a 1.0 mL or 2.0 mL fill volume in a 3 cc glass vial, as a 50 mg/mL solution containing 25 millimolar (mM) histidine/histidine-hydrochloride, 205 mM sucrose and 0.02% (weight/volume) polysorbate 80, at a pH of 6.0. CDX-3379 is manufactured in accordance with Good Manufacturing Practices (GMP) and labeled according.

5.1.2 Trametinib (Mekinist®)

Trametinib tablets (also referred to as GSK1120212B Tablets, TMT212-NXA Tablets) are immediate release tablets for oral administration containing trametinib dimethyl sulfoxide (GSK1120212B/TMT212-NXA) equivalent to 0.125 mg, 0.5 mg or 2 mg of trametinib (GSK1120212/TMT212, non-solvated parent). Trametinib Tablets, 0.125 mg are dark pink, round, biconvex, film-coated tablets. Trametinib Tablets, 0.5 mg are yellow, modified oval, biconvex, film-coated tablets. Trametinib Tablets, 2 mg are pink, round, biconvex, filmcoated tablets. Trametinib Tablets are packaged into a high density polyethylene (HDPE) bottle that contains desiccant with a child-resistant closure that includes an induction seal liner.

List of Excipients

Tablet Core

- Mannitol
- Microcrystalline cellulose
- Hypromellose
- Croscarmellose sodium
- Magnesium stearate (non-animal)
- Colloidal silicon dioxide
- Sodium lauryl sulfate

Film-coat (aqueous film-coating; water is removed during processing)

- Opadry Red 03B25344 (0.125 mg) containing hypromellose, titanium dioxide, polyethylene glycol, and iron oxide red
- Opadry Yellow 03B120006 (0.5 mg) containing hypromellose, titanium dioxide, polyethylene glycol, and iron oxide yellow
- Opadry Pink YS-1-14762-A (2 mg) containing hypromellose, titanium dioxide, polyethylene glycol, polysorbate 80, and iron oxide red.

All excipients used in the tablet core are standard and of pharmacopoeial quality. The coating pre-mixes (Opadry) are a combination of standard ingredients, which are of pharmacopoeial or international standards' quality.

5.2 Treatment Regimen

CDX-3379 will be given IV at 15mg/kg every three weeks of a 21-day cycle. Trametinib will be given at a dose of 2 mg PO daily. Treatment will continue until disease progression, intolerable side effects, subject choice, or study closure.

CONFIDENTIAL

This material is the property of the NYU School of Medicine and Langone Medical Center. Do not disclose or use except as authorized in writing by the study sponsor

5.3 Method for Assigning Subjects to Treatment Groups

This is an open label, non-randomized study. All subjects with *NRAS* mutant or WT melanoma will be enrolled on the Phase 1B portion of the study. During Phase 2, subjects with *NRAS* mutant or WT melanoma will be enrolled and assigned to their respective study arm – based on mutation status – for the purpose of analysis.

5.4 Preparation and Administration of Study Drug

5.4.1 CDX-3379 Storage and Handling

CDX-3379 is shipped in insulated shippers and must be stored at 2 - 8°C (36 - 46°F) until use. Do not freeze CDX-3379 solutions. A temperature log must be kept to document the refrigerator temperature. If the temperature is not maintained, Celldex should be contacted.

CDX-3379 is not formulated with a preservative. Therefore, once the sterile vials are entered (i.e., needle puncture of the vial), the drug should be used as soon as possible (typically within 3 hours if kept at room temperature or within 6 hours if refrigerated; or in accordance with any applicable institutional guidance). Additional guidance regarding storage and handling of CDX-3379 will be provided on the pharmacy sheet provided by Celldex.

5.4.2 CDX-3379 Administration

The dose of CDX-3379 is 15 mg/kg, administered intravenously every 3 weeks (on day 1 of each 21-day cycle). Subjects will be treated with CDX-3379 until progressive disease, unacceptable toxicity, or other criteria for discontinuation of study treatment.

Subjects will receive CDX-3379 as an IV infusion over 60 ± 5 minutes. As a routine precaution, the investigative site's medical staff is to closely observe patients for the duration of CDX-3379 infusion and for at least 1 hour after the end of the infusion.

The entire contents of the IV bag should be administered through an IV administration set with a low protein binding 0.2-µm in-line filter. Since the compatibility of CDX-3379 with other IV medications and solutions other than normal saline (0.9% [w/v] Sodium Chloride for Injection) is not known, the CDX-3379 solution shall not be infused through an IV line in which other solutions or medications are being co-administered. The date, start time, interruption, and completion time of CDX-3379 administration must be recorded in the source documents.

5.4.3 Trametinib Storage and Handling

The recommended storage conditions, shelf-life and expiry date, where required, are stated on the product label. Trametinib will be provided as 0.5 mg and 2 mg tablets. Trametinib tablets must be kept refrigerated.

5.4.4 Trametinib Administration

Trametinib will be administered orally daily at 2 mg (on an empty stomach either one hour prior to or two hours after eating). On days where the subject receives both CDX-7739 and trametinib, the subject will take trametinib immediately following infusion of CDX-3379 (on an empty stomach either one hour prior to or two hours after eating). Do not take a missed dose within 12 hours of the next dose. Subjects are expected to be treated until investigator assessed progressive disease is noted, in the event of unacceptable toxicity, subject choice, or study closure.

5.5 Subject Compliance Monitoring

CDX-3379 will be administered by study staff, and details regarding each administration will be recorded in the subject's medical record and the CRFs. Trametinib will be self-administered, and a medication diary will be provided to subjects.

CONFIDENTIAL

This material is the property of the NYU School of Medicine and Langone Medical Center. Do not disclose or use except as authorized in writing by the study sponsor

5.6 **Prior and Concomitant Therapy**

No other investigational agents or concurrent therapy for melanoma will be allowed during treatment on this clinical trial.

There are no restrictions on the number of prior therapies, however, subjects may not have been treated previously with an ERBB3 or MEK inhibitor.

Drug Interactions: No formal drug interaction studies have been conducted with trametinib. Trametinib is not a substrate of CYP enzymes or efflux transporters P-gp or BCRP *in vitro*. Based on *in vitro* studies, trametinib is not an inhibitor of CYP450 including CYP1A2, CYP2A6, CYP2B6, CYP2C9, CYP2C19, CYP2D6, and CYP3A4 or of transporters including OATP1B1, OATP1B3, P-gp, and BCRP at a clinically relevant systemic concentration of 0.04 µM. Trametinib is an inhibitor of CYP2C8 *in vitro* (trametinib package insert).

Trametinib is an inducer of CYP3A4 *in vitro*. Based on cross-study comparisons, oral administration of trametinib 2mg once daily with everolimus (sensitive CYP3A4 substrate) 5 mg once daily, had no clinically important effect on the AUC and C_{max} of everolimus (trametinib package insert).

In general, concomitant medications and therapies deemed necessary for the supportive care (e.g., such as anti-emetics, anti-diarrhea) and safety of the subject are allowed.

Subjects are permitted to use the following medications during study treatment:

- Medications to prevent or treat nausea or vomiting.
- Anti-diarrheal medications (e.g., loperamide) for subjects who develop diarrhea.
- Pain medication to allow the subject to be as comfortable as possible.
- Bone targeted therapies (e.g., bisphosphonates, denosumab) to treat bone metastases or to prevent skeletal related events.
- Palliative radiotherapy: any radiotherapy must be listed on the 'Surgical and Medical Procedures' eCRF.
- Immunosuppressive agents to treat suspected AEs.
- Nutritional support or appetite stimulants (e.g., megestrol).
- Oxygen therapy and blood products or transfusions.
- Limited-field palliative radiotherapy to non-target lesion(s) may be allowed as concomitant therapy. Such local therapies administered during the study treatment
- Inactivated vaccines.
- The subject must be told to notify the investigational site about any new medications he/she takes after the start of the study drug. All medications (other than study drug) and significant non-drug therapies (including physical therapy, herbal/natural medications and blood transfusions) administered during the study must be listed on the Concomitant Medications or the Procedures and Surgical and Medical Procedures eCRF.

5.7 **Blinding of Study Drug**

This is an open label, non-randomized study. There is no blinding of treatments.

5.8 **Receiving, Storage, Dispensing and Return**

5.8.1 **Receipt of Drug Supplies**

Upon receipt of the of the study treatment supplies, an inventory must be performed and a drug receipt log filled out and signed by the person accepting the shipment. It is important that the designated study staff counts and verifies that the shipment contains all the items noted in the shipment inventory. Any damaged or unusable study drug in a given shipment (active drug or comparator) will be documented in the study files. The investigator must notify study sponsor of any damaged or unusable study treatments that were supplied to the investigator's site.

CONFIDENTIAL

